#### **10.4.** Appendix 4: Treatment States and Phases

#### 10.4.1. Treatment States

Assessments and events will be classified according to time of occurrence relative to the randomization date and study treatment stop date.

#### 10.4.1.1. Treatment States for Hgb Data

Treatment State	Definition
Pre-therapy	Date ≤ Randomization Date
On-therapy	Randomization Date < Date ≤ Study Treatment Stop Date + 1 day
Post-therapy	Date > Study Treatment Stop Date + 1 day

NOTES:

• If Randomization date is missing then the assessment will be consider to be Pre-therapy

• If study treatment stop date is missing then the assessment will be considered to be On-therapy

#### 10.4.1.2. Treatment States for AE Data

Treatment State	Definition
Pre-therapy	AE Start Date < Randomization Date
On-therapy	If AE onset date is on or after randomization date & on or before Study Treatment Stop Date + 1 day
	Randomization Date ≤ AE Start Date ≤ Study Treatment Stop Date + 1 day
Post-therapy	If AE onset date is after Study Treatment Stop Date + 1 day
	AE Start Date > Study Treatment Stop Date + 1 day
Duration (Days)	AE Resolution Date – AE Onset Date + 1 day
Drug-related	If relationship is marked 'YES' on eCRF or value is missing.

#### NOTES:

• If Randomization date is missing then the assessment will be consider to be Pre-therapy

• If study treatment stop date is missing then the AE will be considered to be On-therapy.

#### 10.4.1.3. Treatment States for Concomitant Medications Data

Treatment State	Definition
Pre-therapy	Concomitant Medication Start Date ≤ Randomization Date
On-therapy	Define as (A) or (B)
	(A): If concomitant medication start date is on or after randomization date & on or before Study Treatment Stop Date
	
 
Randomization Date ≤ Concomitant Medication Start Date ≤ Study Treatment Stop Date
 

	If Study Treatment Stop Date is missing, just check if the start date is on or after randomization date. (B): If concomitant medication start date is before randomization date & concomitant medication stop date is on or after randomization date
	Concomitant Medication Start Date < Randomization Date

Treatment State	Definition				
	
 
Randomization Date ≤ Concomitant Medication Stop Date
 
				
Post-therapy	Concomitant Medication Stop Date > Study Treatment Stop Date				
	If Study Treatment Stop Date is missing:				
	
 
post-therapy = blank
 
				
	where Concomitant Medication Stop Date $\geq$ Randomization Date				
	
 
post-therapy = Y
 
				
	where concomitant medication stop date are missing				
	
 
post-therapy = N
 
				
	where Concomitant Medication Stop Date < Randomization Date				

NOTES:

- If Randomization date is missing then the assessment will be consider to be Pre-therapy
- Data of concomitant medication includes ESA, iron, and blood products and blood supportive care products.

	Pre- therapy		On-therapy		Post-therapy		Pre-therapy medication	On-therapy medication	Post-therapy medication
(a)	xx				ys		Y	Ν	N
(b)	x		——Х	~	Da		Y	Y	N
(C)	x			)ate	+ 1	X	Y	Y	Y
(d)		)ate	xx	p [	ate -		Ν	Y	N
(e)		n D	Х——	Stc	Da	———Х	Ν	Y	Y
(f)		atio		ent	top	xx	Ν	Ν	Y
(g)	?—— x	niz		tme	nt S		Y	Ν	N
(h)	?	dor	——Х	rea	ner		Y*	Y	N
(i)	?	kan		уT	eatr	———Х	Y*	Y*	Y
(j)	x	Ľ.		tud	Tr	?	Y	Y**	Y**
(k)			x	S	лdу	?	Ν	Y	Y**
(I)					Sti	x——?	Ν	Ν	Y
(m)	?———					?	Y***	Y***	Y***
(n)	x	х					Y	Y	N
(0)	?	х					Y*	Y	N
(p)		х	——Х				Ν	Y	N
(q)		х		х			Ν	Y	N
(r)				х		———Х	Ν	Y	Y
(s)				х		?	Ν	Y	Y**
(t)					х	———Х	N	Ν	Y
(u)					х	?	N	Ν	Y
(v)			Х——	—	х		N	Y	Y

Illustrations of the pre-therapy, on-therapy, and post-therapy treatment states for concomitant medications are included below:

x = start/stop date of medication

? = missing start/stop date of medication

\* If a medication is stopped On-therapy or Post-therapy and no start date is recorded it will be assumed that the medication was ongoing from the Pre-therapy phase

\*\* If a medication is started Pre-therapy or On-therapy and no stop date is recorded then usage will be assumed to be ongoing for the remainder of the study

\*\*\* If a medication has no start or stop date it will be assumed that the medication was ongoing from the Pretherapy phase to the Post-therapy phase

# 10.5. Appendix 5: Data Display Standards & Handling Conventions

#### 10.5.1. Study Treatment & Sub-group Display Descriptors

Treatment Group Descriptions					
RandAll NG Data Displays for Reporting					
Code	Description	Description	Order		
D1	GSK1278863	GSK1278863	1		

#### 10.5.2. Baseline Definition & Derivations

#### 10.5.2.1. Baseline Definitions

The baseline value will be the latest pre-dose assessment. This is generally expected to be the pre-dose value from the Day 1 visit, except for ECG. For ECG, screening assessment will be used as a baseline.

For vital signs, the baseline value at pre- and post-dialysis will be defined differently.

#### 10.5.2.2. Derivations and Handling of Missing Baseline Data

Definition	Reporting Details
Change from Baseline	= Post-Dose Visit Value – Baseline
Change from Baseline For Vital Signs	
 
Pre-dialysis:         
 
Post-Dose Visit Value from Pre-Dialysis Assessment – Baseline from Pre-Dialysis Assessment
 
 
 
Post-dialysis:         
 
Post-Dose Visit Value from Post-Dialysis Assessment – Baseline from Post-Dialysis Assessment
 
 
 

% Change from Baseline For TSAT, Hepcidin, and Lipid Parameters	
 
Log-transform the data at both the baseline and the specified timepoint
 
Calculate a change from baseline using the log-transformed data for each subject
 
Calculate the mean, and 95%Cl and standard error (SE) of the log-transformed data
 
Exponentially back-transform to the original scale
 
Subtract 1, then multiply everything by 100%
 
So, geometric mean for percent change from baseline         = { exp(Mean [ln(Post-Dose Visit Value) – ln(Baseline)]) – 1 }x         100
 

204716

#### CONFIDENTIAL

Definition	Reporting Details
	Coefficient of variation will be calculated as
	CV%=[exp(Var in log scale)-1 ] 1/2 x 100
	where 'Var in log scale' represents variance of percent change
	from baseline in log scale.

NOTES :

- Unless otherwise specified, the baseline definitions specified in Section 10.5.2.1 will be used for derivations for endpoints / parameters and indicated on summaries and listings.
- Unless otherwise stated, if baseline data is missing, no derivation will be performed and will be set to missing.

### 10.5.3. Reporting Process & Standards

Reporting Process					
Software					
The currently sup	• The currently supported versions of SAS software and S-Plus will be used.				
Reporting Area					
HARP Server : uk1salx00175					
HARP Area	: /arenv/arprod/gsk1278863/mid204716/final_01				
QC Spreadsheet	: /arenv/arprod/gsk1278863/mid204716/final_01/documents				
Analysis Datasets					

 
Analysis datasets ADaM IG Version
 
	
 
Analysis datasets will be created according to CDISC standards (SDTM IG Version 3.1.3 & ADaM IG Version 1.0.
 
				

 
For creation of A implemented for
 
	• For creation of ADaM datasets (ADCM/ADAE), the same version of dictionary datasets will be implemented for conversion from SI to SDTM.				
Generation of RTF Files					
Not generated.					
Reporting Standards					
General					

 
The current GSK Integrated Data Standards Library (IDSL) will be applied for reporting, unless otherwise stated:
 
					

 
4.03 to 4.23: General Principles
 
					

 
5.01 to 5.08: Principles Related to Data Listings
 
					

- o 6.01 to 6.11: Principles Related to Summary Tables
- 7.01 to 7.13: Principles Related to Graphics

#### Formats

- All data will be reported according to the actual treatment the subject received unless otherwise stated.
- GSK IDSL Statistical Principles (5.03 & 6.06.3) for decimal places (DP's) will be adopted for reporting of data based on the raw data collected.
- Numeric data will be reported at the precision collected on the eCRF.

#### Planned and Actual Time

Reporting Standard	s					
Reporting for tab	Departing for tables, figures and formal statistical analyses:					
Planned time	
 
Planned time relative to dosing will be used in figures summaries statistical analyses and
 
					
calculation of	calculation of any derived parameters, unless otherwise stated.					
For Individua	For Individual PK figures, the plot will use actual relative time.					

 
The impact of visit days on
 
	f any major deviation from the planned assessment times and/or scheduled the analyses and interpretation of the results will be assessed as appropriate.					
Reporting for Dat	ta Listings:					
Planned and     IDSL Statistic	actual time relative to study drug dosing will be shown in listings (Refer to cal Principle 5.05.1).					
Unscheduled	l or unplanned readings will be presented within the subject's listings.					

 
Scheduled vi
 
	sits outside the protocol defined time-windows (i.e. recorded as protocol					
deviations) w	ill be included in listings, figures, summaries and statistical analyses.					
Unscheduled Visits						
Unscheduled visit	ts will not be included in summary tables, unless otherwise specified.					

 
If unschedule
 
	ed visits are included in a summary, it will be provided how a summary will be					
produced as	appropriate.					
Unscheduled visit	ts will not be included in figures, unless otherwise specified.					
All unscheduled	visits will be included in listings.					
Descriptive Summa	ry Statistics					
Continuous Data	Refer to IDSL Statistical Principle 6.06.1: This does not apply to the output of statistical models or when the standard list is inappropriate.					
	• Hgb and iron summary statistics will include 95%CI and percentiles (P25 and P75).					
	• Dose level and dose adjustment frequency summary statistics will include mode.					
Categorical Data	N, n, frequency, %					
Reporting of Pharm	acokinetic Concentration Data					
Descriptive	Descriptive Refer to IDSL Statistical Principle 6.06.1					
Summary Statistics Assign zero to NQ values (Refer to GUI_51487 for further details)						
Reporting of Pharmacokinetic Parameters						
Descriptive N, n, geometric mean, 95% CI of geometric mean, standard deviatior						
Summary Statistics of log-transformed data and between geometric coefficient of variation (CV						
(Log Transformed)	(%)) will be reported.					
	[1] $CV_b$ (%) = $\sqrt{\exp(SD^2) - 1} * 100$					
	(SD = SD of log transformed data)					
Graphical Displays						
Refer to IDSL Sta	atistical Principals 7.01 to 7.13.					

# **10.6.** Appendix 6: Derived and Transformed Data

### 10.6.1. General

Multiple Measurements at One Time Point			
• Mean of the measurements will be calculated and used in any derivation of summary statistics but if listed, all data will be presented.			
• Subjects having both High and Low values for Normal Ranges at any post-baseline visits for safety parameters will be counted in both the High and Low categories of "Any visit post-baseline" row of related summary tables. This will also be applicable to relevant Potential Clinical Importance summary tables.			
• For multiple measurements at Screening and Day 1 visit, the screening-pass visit record will be used for analysis (See Appendix 3).			
Study Day			

 
Calculated as the number of days from randomization date:
 
Ref Date = Missing → Study Day = Missing
 
Ref Date < Randomization Date → Study Day = Ref Date - Randomization Date → Study Day = Ref Date - (Randomization Date) +1
 
			
Unique Subject ID			

 
All subjects have unique subject ID for analyses even if a subject was enrolled after rescreened. Tables/figures/listings will be produced based on unique subject ID.
 
For a rescreened subject, the unique subject ID will be derived from the first-assigned subject number though he or she seems to have multiple subject numbers in eCRF records by screening assessment. The other subject numbers, which are to be recorded within a supplemental domain, will be associated with the unique subject ID.
 
			
Rescreening Subjects			

 
For rescreened subjects, data collected in screening-pass visit will be used for analysis. They may have multiple records at Screening and/or Day 1 visit, which associates with a screening-pass visit and screening failure visit(s)
 
Regarding a listing of SAEs in screening period, all pre-therapy SAEs captured in eCRF will be provided including screen failure records of rescreened subjects.
 
			
Study Treatment Start Date			
First randomized treatment start date			
Study Treatment Stop Date			
Latest end date of treatment			
• Note that the end date of treatment will be captured as the end date when subjects were intended to end the treatment, rather than when subjects have actually ended the treatment.			
Time Definitions (per GSK standard principles)			

 
1 week = 7 days
 
1 month = 30.4375 days
 
1 year = 365.25 days
 
			

#### 10.6.2. Study Population

Subject Disposition and Study Population
 Screening status and reason for screening failure for a subject who has multiple subject numbers will be unique in the unique subject ID.

- The screening status of a subject who failed screening but passed rescreening will be 'enrolled', and the reason for failure will not be counted.
- The screening status of a subject who failed more than one screening and never passed will be 'failed', and the reason for failure will be derived from the latest failure record.
- Study population of subjects will be derived from the above unique screening status.

#### **Demographics and Baseline Characteristics**

#### Age

- GSK standard IDSL algorithms will be used for calculating age where birth date will be imputed as follows:
  - $\circ~$  A date and month will be imputed as '30th June' as it will not be captured.
- Randomization date will be used as reference date of calculation.
   If randomization date is missing, screening date will be used.

#### Body Mass Index (BMI)

• Calculated as Weight (kg) / [Height (m)]

#### Exposure

#### Prescribed Dose and Actual Dose

- Prescribed dose will be derived from a dose record captured in eCRF.
- In principle, actual dose will be the same as prescribed dose except for a case in which inconsistency between a prescribed dose and prescribed bottle(s) occurs. If such an inconsistency case (e.g. wrong treatment) is detected by study team, the actual dose may be replaced with a plausible value by case-by-case review.

#### Extent of Exposure

- Number of days of exposure to study drug will be calculated based on the formula: Duration of Exposure in Days = Sum of [Exposure Duration at Each Visit] where Exposure Duration at Each Visit = Treatment Stop date - Treatment Start date + 1 If dose is interrupted in a visit according to dose adjustment algorithm, duration in the period will be included in duration of exposure.
- Cumulative dose will be based on the formula using prescribed dose: Cumulative Dose = Sum of (Exposure Duration x Dose) at Each Visit
- Daily Dose
  - Cumulative Dose / Duration of Exposure in Days

#### Treatment Compliance

Listing will include treatment compliance up to Week 4 and overall.
 Overall Compliance(%) = [(Total # of tablets actual taken)/(Total # of tablets planned)

Exposure				
taken)]*100				
Compliance (%) up to Week 4 = [(# of tablets actual taken up to Week 4)/(# of tablets planned				
taken up to Week 4)]*100				
where				
Total # of tablets actual taken = Sum of (Numbers of Tablets Taken at Each Visit)				
Total # of tablets planned taken = Sum of [(Treatment Stop Date – Treatment Start Date + 1) x Planned # of tablet/day in the Visit]				
# of tablets actual taken up to Week 4 = Numbers of Tablets Taken of Day 1 record				
# of tablets planned taken up to Week 4= (Treatment Stop date of Day 1 record – Treatment				
Start Date of Day 1 record + 1)				
Planned # of tablet/day is defined as follows according to the protocol:				
$\circ$ 0 mg $\rightarrow$ 0 tablet/day				
○ 1 mg $\rightarrow$ 1 tablet/day				
$\circ$ 2 mg → 1 tablet/day				
○ 4 mg → 1 tablet/day				
$\circ$ 6 mg → 1 tablet/day				
$\circ$ 8 mg → 2 tablets/day				
○ 12 mg $\rightarrow$ 2 tablets/day				
$\circ$ 18 mg → 3 tablets/day				
$\circ$ 24 mg → 4 tablets/day				
where dose records are derived from prescribed doses.				

# 10.6.3. Efficacy

Hgb Values for Efficacy Analyses				
Central laboratory and HemoCue Hgb Values				
• For reporting purposes, central laboratory Hgb values will be used, unless otherwise specified. However, if a central laboratory Hgb value is missing, a corresponding non-missing HemoCue Hgb value, which is associated with the identical subject number and visit, will be used.				
Evaluable Hgb Values				
• Note that this will not be applicable for reporting summaries and figures, but applicable for reporting listings.				

 
Evaluable Hgb values will be based on on-therapy central laboratory and/or HemoCue Hgb values that are not taken within the 8 weeks following a transfusion or within the 8 weeks following a non-randomized ESA medication (except protocol-specified ESA treatment in screening period).
 
				
evaluable Hgb = 'N'.				

 
Blood Product Administration Date < Date of Hgb data ≤ Blood Product Administration Date + 56 (days)
 
				

corresponding HemoCue measurement) will be used. The figure will include Pearson's

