6.10.1. Permitted Medications and Non-Drug Therapies

Unless specified as a prohibited medication in Section 6.10.2, all concomitant medications should be considered permitted provided they are not contraindicated for the individual subject concerned.

Regular multivitamins (at recommended daily allowance) and other supplements such as calcium and vitamin D may be used if permitted by the investigator or his/her designee.

CYP2C8 is involved in the primary route of metabolism of GSK1278863. Accordingly, co-administration of GSK1278863 with moderate CYP2C8 inhibitors (e.g., clopidogrel, teriflunomide, deferasirox) should be performed with caution. If one of these medications is started, stopped or the dose is changed, Hgb should be monitored every 4 weeks for 12 weeks using a point-of-care Hgb analyzer (Hemocue).

Antihyperphosphatemic agents containing iron (e.g., ferric citrate hydrate) may be started from Week 4 onwards unless any other antihyperphosphatemic agents are appropriate. Once started, iron-containing antihyperphosphatemic agents should be continued until the end of the study wherever possible.

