Dose level (mg) at each assessment visit			Y	Y		
by Dialysis Status			N			
>13.0 g/dL [3]			Y			
Duration (days) of treatment interruption due to Hgb			Y			
>13.0 g/dL [3]						
by Dialysis Status						
Dose adjustment			Y			
Dose adjustment			Y			
by Dialysis Status						
Number (%) of subjects with each dose level at each			Y			
assessment visit						
Number (%) of subjects with each dose level at each			Y			
assessment visit						
by Dialysis Status						
Number of dose adjustment to reach the lower Hgb target			Y			
Hgb level (10.0 g/dL)			N			
Number of dose adjustment to reach the lower Hgb target			Y			
Hgp level (10.0 g/dL)						
by Dialysis Status						
Uther				V		
Scaller plot of change from baseline in Hgb at week 4 Vs.				ľ		
Cantuluate Covariates [0]				V		
Scaller plot of mean dose vs. candidate covariates [6]		1		Υ		

NOTES :

[1] Not only within the target range, but also subjects with above and below target range will be assessed.
[2] Time to first reach the lower target Hgb level will be estimated by Kaplan-Meier method using P25, median and P75. Subjects who could not reach lower target will be regarded as censored.

Endpoint / Parameter/ Display Type			Abso	olute		
	Stats A	nalysis	Summary		Individual	
	Т	F	Т	F	F	L

[3] On-therapy Hgb values observed in scheduled visits will be included. On-therapy Hgb values observed in unscheduled visits will be included if specified (see Section 8.1.2)

[4] Based on literature review the distributions of TSAT and hepcidin are skewed and require a log-transformation.

[5] Summaries for dose adjustment will be based on HemoCue Hgb values including those of unscheduled visits.[6] Figures will include the candidate covariates of body weight and baseline Hgb, and will be produced for overall and dialysis status groups.

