#### Secondary Hgb Analyses

range as secondary endpoints.

- For the Hgb, the summary statistics will be calculated, along with the two-sided 95% confidence interval based on t-distribution.
- The percentage of subjects with Hgb within the target range will be calculated at Week 24, with calculation of exact two-sided 95% confidence interval based on binomial distribution.
- The time (in days) to reach first the lower target Hgb level (10.0 g/dL) will be calculated in each subject, and summarized descriptively by Kaplan-Meier method using P25, median, and P75. Subjects who could not reach lower target will be regarded as censored at Study Treatment Stop Date (See Section 10.6.1).

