# 10.1. Appendix 1: Protocol Deviation Management and Definitions for Per Protocol Population

Per Protocol Population will not be defined in this study.

204716

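### SAP 10.6.3 flags Hgb within 8 weeks after a transfusion or ESA as not evaluable but uses the flag in listings only, so in subjects kept on study drug these values enter the Hgb summaries with no sensitivity analysis

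*SAP*

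**What the plan says.** SAP 10.6.3 defines evaluable Hgb as on-therapy central laboratory or HemoCue values "not taken within the 8 weeks following a transfusion or within the 8 weeks following a non-randomized ESA medication", with an exception for ESA treatment that the protocol specifies in screening. For blood products the window is written as a date rule of 56 days. The scope is then restricted: "Note that this will not be applicable for reporting summaries and figures, but applicable for reporting listings".

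Nothing else in the plan takes these values out of the tables:

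- On-therapy status (SAP 10.4.1.1) runs from the randomization date to the limit "Date ≤ Study Treatment Stop Date + 1 day". Rescue treatment does not end it.
- SAP 10.7.1 puts all available planned data into tables and figures. SAP 10.7.2.2 allows only one substitution, HemoCue for a missing central value.
- SAP 10.1: "Per Protocol Population will not be defined in this study".
- For time to 10.0 g/dL, Table 4 note [3] of the SAP says: "On-therapy Hgb values observed in scheduled visits will be included".
- For the target range, SAP 8.1.3 says: "The percentage of subjects with Hgb within the target range will be calculated at Week 24", with an exact binomial interval.

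On rescue itself, Protocol 6.10.2 prohibits ESAs to the end of the treatment period and does not mention transfusion. Protocol 6.10.1 reads: "Unless specified as a prohibited medication in Section 6.10.2, all concomitant medications should be considered permitted". SAP 10.4.1.3 counts blood products as concomitant medication. Protocol 5.4 and Table 5 stop study drug permanently at Hgb below 7.5 g/dL. Transfusion is not a withdrawal criterion. The prohibited-medication criterion in 5.4 concerns use beyond 14 days and names only CYP2C8 drugs.

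The SAP does tabulate and list on-therapy ESA and blood-product use (Tables 1.23 to 1.26, Listings 34 and 36).

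**The concern.** The objectives are to describe the starting-dose response and overall Hgb control on GSK1278863 in patients not using ESAs. A subject who is transfused and stays on drug may be counted as within 10.0 to 12.0 g/dL, or as having reached 10.0 g/dL, because of the transfusion. The same rise may instead place the subject above 2 g/dL over 4 weeks or above 13.0 g/dL, which counts against the drug. The SAP recognises that such values are not informative about the drug and derives a flag for them, yet no planned output shows what they do to an estimate. With about 22 subjects each case can be traced in the listings. To see the effect, though, a reader would have to rebuild the t intervals, exact intervals and Kaplan-Meier quartiles by hand.

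**Working it through.** **Inputs from the documents.** Week 4: n = 20, SD 1.5 or 1.0 g/dL (Protocol 9.2.1, Table 9). Week 24: n = 17 (Protocol Table 1). Flag: administration date < Hgb date ≤ administration date + 56. This formula is legible for blood products only; for ESAs the 8 weeks stated in words are used. Nominal visit days: 29 for Week 4, 169 for Week 24.

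**Assumed, because the documents give no rescue rate or effect.** One to three flagged subjects; a flagged value 0.5 to 1.5 g/dL away from the mean of the others; 10 of 17 in range at Week 24.

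**1. The plan's own precision figure.** Half-width = t(0.975, n−1) × SD/√n. With n = 20 and SD 1.5 this gives 0.702 g/dL, as Protocol 9.2.1 states. All six cells of Table 9 reproduce.

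**2. When the flag applies.** Counting from Day 1, an administration on Days 1 to 28 flags Week 4. An administration on Days 113 to 168 flags Week 24: 56 of 168 treatment days, or 33%. Read literally, the rule also flags Week 4 for a transfusion in the 28 days before Day 1. That transfusion is already in the baseline, which is the latest pre-dose value (SAP 10.5.2.1). If anything it lowers the measured change, so it is not counted here.

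**3. Week 4.** One value at distance d from the mean of the others moves the mean of 20 by d/20: 0.5/20 = 0.025 and 1.5/20 = 0.075 g/dL. The larger figure is 0.075/0.702 = 11% of the planned half-width. In the category table each subject is 1/20 = 5 points.

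**4. Week 24 target range.** Planned result under the assumption: 10/17 = 58.8% (exact 95% CI 32.9 to 81.6).

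| Flagged subjects | In range, excluded | Below range, excluded | In range, counted as not in range |
|---|---|---|---|
| 1 | 9/16 = 56.3% | 10/16 = 62.5% | 9/17 = 52.9% |
| 2 | 8/15 = 53.3% | 10/15 = 66.7% | 8/17 = 47.1% |
| 3 | 7/14 = 50.0% | 10/14 = 71.4% | 7/17 = 41.2% |

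The last column falls by 1/17 = 5.9 points per subject, whatever the starting percentage. Exclusion alone moves the result by anything from −8.8 to +12.6 points. It rises when the excluded subjects were poor responders, so an evaluable-only table is not enough by itself.

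**5. Time to 10.0 g/dL.** Illustration with assumed counts: 22 subjects, 8 reach the level at Week 4 and 6 at Week 8, and one subject is rescued between these visits. Planned: 14/22 = 63.6% by Week 8.

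- Rescued subject is one of the 6: non-event gives 13/22 = 59.1%; censoring at Week 4 gives 1 − (14/22)(8/13) = 60.8%.
- Rescued subject did not reach the level: non-event stays at 63.6%; censoring gives 1 − (14/22)(7/13) = 65.7%.

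Censoring can therefore raise the estimate when the rescued subject was doing badly. The non-event run cannot.

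**The case against.** Five arguments run the other way.

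- **The choice is explicit and defensible.** The SAP states the scope openly. Using all data regardless of rescue can be read as a treatment-policy summary, and there is no hypothesis test or success threshold for these values to cross. This stands, and it is why the planned tables should remain the main result. The SAP does not give that reasoning, however, and plans no sensitivity analysis.
- **The 7.5 g/dL stop covers the anaemia most likely to prompt rescue.** After stopping, no scheduled treatment visits remain to feed the by-visit tables. This stands and narrows the point to subjects rescued while still on drug.
- **ESA use is a deviation.** SAP 4.1 requires a pre-freeze review of important deviations, with a summary and listing (Table 1.6, Listing 4). This stands. It makes a case visible but does not remove its Hgb values, and it does not cover a permitted transfusion.
- **The effect is assumed and lies well inside the confidence interval.** This stands on the assumption, but a shift within a wide interval is still worth showing.
- **Use is already listed, and Figure 2.11 plots each subject's Hgb and dose.** This stands for traceability, not for the estimates.

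A reader might infer that the rule inflates the drug's apparent effect. The documents do not support that. The primary analysis looks for a rise of no more than 2 g/dL (Protocol 9.4.1.1), so a transfusion-driven rise can move a subject into the unfavourable category. A reader might also infer that a screening-period transfusion creates a false Week 4 response; it does not, because it is already in the baseline.

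**Conclusion.** The point holds in a limited form. For a subject who is rescued and stays on study drug, the plan counts values that its own definition calls not evaluable, and no output shows their effect. This is a cheap improvement to a design choice rather than an error that undermines the study. The direction is not fixed.

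The effect is nil without rescue and small for the Week 4 mean (0.025 to 0.075 g/dL per subject). It matters mainly for the Week 24 target-range percentage (5.9 points per in-range flagged subject counted as not in range, n = 17) and for time to 10.0 g/dL. The number of flagged subjects, the 10/17 and the size of the Hgb differences are assumptions. In the SAP text as supplied, the detailed derivations of time to 10.0 g/dL and of the rise above 2 g/dL cannot be read in full. The scope note on summaries and figures is general and does not depend on them.

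**What to change.** Keep every planned table as the main result. Add the following to the SAP, to be produced only if an on-treatment transfusion or ESA flags a post-baseline Hgb value:

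1. Evaluable-only versions of Tables 2.1, 2.3, 2.5 and 2.7, and of the tables for a rise above 2 g/dL and Hgb above 13.0 g/dL (2.13 and 2.15). Leave baseline as planned.
2. A second version of Table 2.7 that counts flagged subjects as not in range.
3. For Table 2.9, a sensitivity run that treats subjects as non-events after first rescue, kept to their treatment stop date. Censoring at the last scheduled Hgb before rescue (Day 1 if none) is an optional second run.

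For these outputs, start the flag from administrations on or after Day 1.

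The cost is seven conditional tables and one or two Kaplan-Meier runs, from a flag the SAP already derives, and nothing if nobody is flagged. No new data, visits or protocol change are needed. The downside is wider intervals in the evaluable-only tables. If 1, 2 or 3 of 20 are excluded at Week 4, the half-width goes from 0.702 to 0.723, 0.746 or 0.771 g/dL (SD 1.5), or from 0.468 to 0.482, 0.497 or 0.514 g/dL (SD 1.0).
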